8. For multi-center studies, number of participants approved for accrual study-wide (University of Alabama site plus all other sites).	
9. For multi-center studies, number of participants enrolled study-wide (University of Alabama site plus other sites).	
10. Number of withdrawals from the research (since last approval date) and explanation/reasons for withdrawals.	
11. Description and number of:	

a) Reportable Protocol Deviations/Violations since the last approval date:

0

b) Serious Adverse Events (SAEs) or unanticipated problems involving risks to participant or others since the last approval date:

0

12. Have there been any complaints about the research during the last year? N
If yes, please describe.

13. **Briefly describe the progress of the study to date.**

Data collection has been completed. Analysis is underway.

14. Is there a Data Safety Monitoring (DSM) plan for this study?

No

Yes, a copy of the DSM report(s) for the last approval period is attached.

Yes, but a copy of the DSM report(s) for the last approval period is not attached. Please explain below.

15. FDA Regulated Studies

Is this a Food and Drug Administration (FDA) Regulated Study, (i.e., N
involves drugs, devices, biologics)? If yes, please answer the following
questions:

a) Have there been any changes in the FDA status
of any drug or device used in the study?

If yes, please explain:

b) Have any of the investigational drugs or devices
used in this study received FDA approval?

If yes, please explain:

c) Have any new alternative drugs or devices been
approved for treatment of the study condition that
may affect participants willingness to participate?

If yes, please explain:

Have current participants been notified? Please explain:

- d) Has there been a change in the standard care that may be considered as an alternative to the investigational drug or device or that would affect the original study design?

If yes, please explain:

Have current participants been notified? Please explain:

- e) Is there any new information that might affect the risk/benefit ratio and the willingness of current study participants to participate or to continue to participate in the research?

If yes, please explain:

Have current participants been notified? Please explain:

- f) Is there any new information about study as a whole, the drug, or device that needs to be provided to past participants

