Mixed Design (Between/Within Subjects) Pre-test/Post-test Comparison

d) **Provide a timeline for individual participant recruitment and follow-up (analysis for the study is required).**

Participants will be recruited from various sources including the UA Participant Registry, DS Connect (NIH Registry of individuals with Down syndrome interested in research), local schools, and local service providers. Following initial contact by these various sources, participant families will self-identify to receive additional information about the study - including a copy of the Parental Consent. The study will take place over the course of 4 months for each participant. All participants will receive the PPVT, the KBIT 2 Matrices subtest, an assessment of Mental Rotation, and an assessment of Visual Perspective Taking during the first testing session (Approximately 45 minutes). Mental Rotation and Perspective Taking performance will be assessed two additional times for all participants, once following Experience Session 16 and once following Experience Session 32. These two assessments will take approximately 15 minutes. Experience sessions will be provided twice per week, with each session lasting approximately 30 minutes over a period of 16 weeks. Half of each group (No Delay participants) will begin spatial ability experience during a first experience session scheduled approximately one week following the initial assessment. The other half of each group (Delay participants) will not begin the spatial ability experience for the 8 weeks following the first assessment and serve as a control for practice effects on the assessment measures. The Delay participants will receive a second assessment on the Spatial Abilities and begin spatial ability experience during week 9. They will receive the same protocol as the experimental participants following the second assessment (8 weeks experience, ability assessment, 8 weeks experience, ability assessment). The final assessment will come following Experience Session 32 (week 16). Data analysis is planned upon the completion of all data collection during year 03 of the

project period.

e) Will participant be randomized? Y

f) If participants will be given placebo, please justify placebo use, and describe contents of the placebo. Y

NA

3) Study Procedures

a) Is this project a multicenter study (i.e., same project is conducted elsewhere by a different investigator)? Y

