Mental Rotation Assessment - On each trial, participants will be presented a geometric shape (e.g., a block letter L) in the center of a computer screen that completes one of two rectangles presented at the bottom of the same screen. The open area in one rectangle is the mirror image of the open area in the second rectangle. The shape in the center of the screen will fit one of the rectangles when horizontal. The shape can be rotated from horizontal by 0, 45, 90, 135, 180, 225, 270, or 315 degrees. Participants respond by touching the rectangle into which the shape will fit once oriented properly (using touchscreen technology). Participants receive 4 trials at each orientation.

Perspective Taking - Participants will be seated at a table with four chairs and four different objects (street lamp, mailbox, stop sign, traffic signal) representing each location on the corner of a city block in front of each chair. A stuffed animal is placed behind each object. One experimenter walks around the table stopping at each location. At each location, the participant is told that the experimenter is taking a picture from that location and he/she is asked to look at four pictures. The task is to select the picture that the experimenter has just taken. The four pictures consist of the participant's point of view, a mirror image of the participant's point of view, the experimenter's point of view, and a mirror image of the experimenter's

Due to CoVid Restrictions, Procedures were adapted for online presentation via Zoom. Ravens and PPVT-4 used available commercial formats. Mental Rotation and Perspective Taking involved the creation of Video presentations. Online presentation was approved by the University IRB on 03/04/2020.

point of view. This task will take 5 - 10 minutes.

Assessments 2 and 3 will include only Mental Rotation and Perspective Taking Assessments.

Spatial Ability Experience will include two tasks of Object manipulation and two Large Environment Experiences. These tasks are meant to provide experience.

Object Manipulation Experience: Two categories of tasks will be used to provide object manipulation experience: LEGO Block Play and Puzzle Construction. One task will be used in each spatial ability experience, with tasks alternating between sessions.

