c) Provide stopping rules for the study. If the proposed study is a clinical trial where a drug, vaccine, device or other treatment is compared to a placebo group or comparison treatment group, what are the guidelines or endpoints by which early decisions regarding efficacy or lack of efficacy can be made? For example, it may be reasonable to stop enrollment on a study when efficacy has already been clearly demonstrated, to avoid unnecessary enrollments of additional participants. Alternatively, it may be reasonable to stop enrollment when it is clear that efficacy will never be demonstrated, given the statistical power of the study as designed. Describe the guidelines that are in place to assist in making these determinations, if relevant to the proposed study.

NA

d) Describe how data analysis will be performed (statistical tests, methods of evaluating data) and indicate the smallest group/unit for which separate reporting will occur. For studies involving a questionnaire, if data and reliability information are available, please describe or provide references. (Page numbers from a sponsor's protocol/grant may be referenced in this section).

The independent variables of interest will be Group (DS and TD), Delay (No Delay and Delay), and Assessment (1, 2, and 3). The smallest number of participants in any given cell of the design is 20 participants.

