Specific Aim 1 evaluates the malleability of MR and PT performance in participants with DS. Consistent with Aim 1, we will apply Multivariate ANOVA to the subsample of DS children. If the test for sphericity is significant, we will interpret the multivariate tests for the within subject effects. If not, we will use the univariate tests due to their increased statistical power. With either option, the test for the effect of Assessment, if significant, would indicate that performance of the DS children improves over time. We will then evaluate the interaction of AssessmentDelay, which if significant would signify that Delay vs No Delay participants exhibit a different magnitude of improvement across Assessment times. One contrast of interest compares Delay vs No Delay participants at Assessment 2. Performance favoring the No Delay participants would indicate a significant effect of spatial ability experience. A second contrast of interest compares Assessment 3 performance to Assessments 1 and 2 for the Delay participants. If we are able to confirm that the Delay participants exhibit higher scores at Assessment 3 than at Assessments 1 and 2 (which should not differ) then the benefits of spatial ability experience for persons with DS would be further confirmed.

Specific Aim 2 evaluates possible differences in rate and magnitude of improvement of DS and TD participants. We will approach Aim 2 in a very similar statistical manner. For Aim 2a, we will apply Multivariate ANOVA to the whole sample to test for the effect of AssessmentGroup. If significant, it is indicative that DS and TD participants do not exhibit the same degree of improvement following training. If improvement in performance is greater for the participants with DS, it

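### The Aim 1 contrast of Delay with No Delay at Assessment 2 is described without baseline adjustment; adjusting for the Assessment 1 score would add precision if the two scores correlate

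*Combined protocol and SAP*

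**What the plan says.** Study Procedures item 3(d) sets out the Aim 1 analysis: "we will apply Multivariate ANOVA to the subsample of DS children". The design factors are listed as "The independent variables of interest will be Group (DS and TD), Delay (No Delay and Delay), and Assessment (1, 2, and 3"), so the Assessment 1 score enters as a level of the repeated factor and not as a covariate.

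The Assessment by Delay interaction comes first, "which if significant would signify that Delay vs No Delay participants exhibit a different magnitude of improvement across Assessment times". The plan then singles out a between-arm comparison: "One contrast of interest compares Delay vs No Delay participants at Assessment 2". A result favouring No Delay is to be read as an effect of spatial experience. Item 3(d) names no adjustment for this contrast. Vocabulary, nonverbal ability and age are planned as correlates of improvement (items 2(a) and 2(b)), not as covariates here.

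The baseline score is available. Under item 2(d), all participants have "an assessment of Mental Rotation, and an assessment of Visual Perspective Taking during the first testing session", before any experience session. Item 2(e) records "Will participant be randomized? Y", and item 2(d) puts half of each group in each arm.

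**The concern.** The Assessment 2 contrast is the only place in Aim 1 where trained and untrained participants with DS are compared directly on a randomised basis. The other named contrast lies within the Delay arm and has no concurrent control. The interaction test does use Assessment 1. However, it has 2 degrees of freedom, it includes Assessment 3, when both arms have been trained, and it gives no single trained-versus-untrained estimate.

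With complete data, an arm comparison at Assessment 2 alone is the raw difference in Assessment 2 means. That difference is unbiased under randomisation. It carries all the between-person variation that the Assessment 1 score could partly explain.

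The DS group is small: 48 were planned, and Continuing Review item 5 reports 30 consented. Adjustment could tighten the estimate without further participants.

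**Working it through.** **Inputs from the documents.** Alpha .05, power .80, 48 DS participants with 24 per arm (Subject Population (m), Section 2(c)); 30 DS participants consented (Continuing Review item 5); 1:1 allocation (item 2(d)).

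**Assumed.** An even split of the 30, so 15 per arm; correlation r between Assessments 1 and 2 from 0 to 0.8; equal SDs at the two assessments; and an illustrative effect of 0.8 SD for power. The documents give no r or SD.

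**The plan's own power figures.** No figure is stated for this contrast.

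- The 4 groups x 3 repetitions statement reproduces. With f(V) = .27 and N = 96, the noncentrality is .27² x 96 x 2 = 14.0 on 6 and 184 df, and power is .797 against the stated .80.
- The N = 48 figures do not reproduce as f(V): power is about 45% for Delay at .27 and 30% for Assessment Time at .25. They come near 80% only if read as Cohen's f with an unstated correlation of about .12 to .13. That is a separate matter and is not evidence of the true r.

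**Formulas, in SD units with n per arm.**

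- Unadjusted: SE = √(2/n), df = 2n − 2.
- ANCOVA: SE = √(2/n) x √[(1 − r²)(1 + 1/(2n − 4))], df = 2n − 3. The last factor is the expected cost of chance baseline imbalance.
- Change score: SE = √(2/n) x √[2(1 − r)], df = 2n − 2.

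Example, n = 15 and r = 0.5: the unadjusted SE is √(2/15) = 0.365. The ANCOVA variance factor is 0.75 x (1 + 1/26) = 0.779, so the SE is 0.365 x 0.883 = 0.322. The detectable effect falls from 1.060 to 0.937 SD, a cut of 1 − 0.937/1.060 = 12%.

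**Results: detectable effect at 80% power, two-sided .05, with the imbalance cost included.** The unadjusted values are 0.826 SD at 24 per arm and 1.060 SD at 15 per arm. Unadjusted power for 0.8 SD at 15 per arm is 56.2%.

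| r | ANCOVA, 24 per arm | ANCOVA, 15 per arm | Cut v unadjusted, 15 per arm | ANCOVA power for 0.8 SD, 15 per arm | Change score, 15 per arm | ANCOVA cut v change score |
|---|---|---|---|---|---|---|
| 0 | 0.836 | 1.081 | 2% worse | 54.5% | 1.499 | 28% |
| 0.2 | 0.819 | 1.060 | 0% | 56.2% | 1.341 | 21% |
| 0.3 | 0.797 | 1.032 | 3% | 58.4% | 1.254 | 18% |
| 0.5 | 0.724 | 0.937 | 12% | 66.8% | 1.060 | 12% |
| 0.7 | 0.597 | 0.772 | 27% | 82.7% | 0.821 | 6% |
| 0.8 | 0.502 | 0.649 | 39% | 93.2% | 0.670 | 3% |

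ANCOVA breaks even with the unadjusted contrast at r of about 0.15 (24 per arm), 0.17 (20 per arm) and 0.20 (15 per arm).

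**Simulation check.** With 100,000 runs at 15 per arm and 0.8 SD, power is 56% unadjusted and 54.8%, 56.5%, 58.3%, 66.8%, 82.8% and 93.3% with ANCOVA at the six correlations. The mean 95% CI half-width is 0.741 SD unadjusted, and 0.756, 0.741, 0.722, 0.655, 0.540 and 0.454 SD with ANCOVA.

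**The case against.** **The plan already uses the baseline, and the contrast may mean change from Assessment 1.** The contrast follows directly on a repeated-measures interaction that contains Assessment 1, and the text does not rule out a change-score reading. On that reading the advantage of ANCOVA is smallest (6% and 3%) at the high correlations where the gain over raw scores looks largest. This limits the size of the claim. It does not remove it, because the wording describes a comparison at Assessment 2, and ANCOVA does better than the change score at every correlation shown.

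**The correlation is unknown and may be low.** This stands. In item 3(b), Mental Rotation has eight orientations and "Participants receive 4 trials at each orientation", so 8 x 4 = 32 two-choice trials. Perspective Taking is described as one picture choice at each of four locations, with no repeats stated. High correlations may be optimistic, especially for the second measure, and the gain may differ between the two. The trade is still favourable: 1 to 2 points of power lost near zero correlation, against about 11 to 37 gained at 0.5 to 0.8 (15 per arm, 0.8 SD).

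**It is late.** Continuing Review item 13 reports "Data collection has been completed. Analysis is underway". If arm comparisons have been seen, an ANCOVA added now is a post hoc analysis. This also stands, and it is why the change needs a dated disclosure.

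**It is analyst preference.** The planned contrast is valid, and nobody claims bias. The point concerns precision only.

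**Conclusion.** The concern holds as a recommended improvement. No baseline adjustment is described for the contrast that carries Aim 1's randomised evidence, the covariate has already been collected, and using it would add precision if the two assessments are more than weakly correlated.

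At 15 per arm the reduction in detectable effect runs from nothing at a correlation of 0.2 to 12% at 0.5 and 39% at 0.8. These sizes rest on an assumed correlation, an even split of the 30 consented participants, and a reading of the contrast as a comparison of Assessment 2 scores. If it is read as change from Assessment 1, the reduction is 21% at 0.2, 12% at 0.5 and 3% at 0.8.

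**What to change.** - For Mental Rotation and Perspective Taking separately, estimate the Assessment 2 contrast by ANCOVA: Assessment 2 score on arm, adjusted for the Assessment 1 score on the same outcome. Include every randomised DS participant who has both assessments.
- Report the adjusted difference with its 95% CI, and show the unadjusted contrast and the planned MANOVA beside it. Report the observed correlation for each outcome so that readers can see what the adjustment gained.
- Date the change and state whether any comparison between arms had been examined by then. If none had, name the ANCOVA as the estimate for this contrast. If one had, label it as added after the fact, so that it does not displace the planned results.

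The cost is a few lines of analysis text, one degree of freedom per model and the dated note. No new data are needed. If the correlation is near zero, about 1 to 2 points of power are lost at 15 per arm.

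### The second Aim 1 contrast (Delay arm, Assessment 3 against Assessments 1 and 2) is uncontrolled and can only support, not confirm, a benefit; which testing is Assessment 3 is also unclear

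*Combined protocol and SAP*

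**What the plan says.** Section 3(d) sets out Aim 1 in sequence: the effect of Assessment, the Assessment-by-Delay interaction, then two contrasts. The first is between the randomised arms: "One contrast of interest compares Delay vs No Delay participants at Assessment 2". The second stays within one arm: "A second contrast of interest compares Assessment 3 performance to Assessments 1 and 2 for the Delay participants". Its reading is that if "the Delay participants exhibit higher scores at Assessment 3 than at Assessments 1 and 2", the latter two being scores "which should not differ) then the benefits of spatial ability experience for persons with DS would be further confirmed".

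Section 2(d) gives the delay period its purpose, which is to "serve as a control for practice effects on the assessment measures". It also fixes when that period ends: "The Delay participants will receive a second assessment on the Spatial Abilities and begin spatial ability experience during week 9".

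On the number of testings, section 2(d) says that the two abilities "will be assessed two additional times for all participants, once following Experience Session 16 and once following Experience Session 32". With the initial assessment that makes three, and sections 3(b) and 3(d) also use three. The same section then gives the Delay arm, after its second assessment, this sequence: "8 weeks experience, ability assessment, 8 weeks experience, ability assessment".

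**The concern.** By Assessment 3 no untrained group is left. A higher Delay-arm score at that point may reflect training, a further practice gain from repeated testing, or both. The delay period was designed to measure practice, yet the plan takes the change over that period to be nil. It does not say how this would be checked, how large a difference would matter, or what follows if the scores differ. Nor does it set the trained change against the untrained change within the arm.

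At stake is the weight a reader gives to the supporting statement. Continuing practice could be reported as confirmation of benefit, and the exposure grows if Assessment 3 turns out to be a fourth testing.

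**Working it through.** The plan states no effect size, retest gain, correlation or error rate for this contrast, so it has no figure to reproduce.

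**Inputs from the documents.** Alpha .05 and 24 participants with Down syndrome per arm (Research Involving Children, Section 2, item c); 30 such participants consented (Continuing Review, item 5).

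**Assumptions.** One outcome score with SD 1; correlation ρ = 0.5 or 0.7 between any two testings; no training effect; the same practice gains in both arms; two-sided 5% tests with the favourable direction counted (nominal 2.5%). The expectation that Assessments 1 and 2 (A1, A2) do not differ is taken as a non-significant test. An equal split of the 30 gives 30/2 = 15 per arm.

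**Step 1: what practice alone contributes.** With gain g at each retest the means are 0, g, 2g. Then A3−A2 = g and A3−(A1+A2)/2 = 1.5g. At g = 0.2 these are 0.2 and 0.3 SD. If practice stops after the first retest (0, 0.2, 0.2), they are 0 and 0.1 SD: the pooled reference still carries half of the first gain.

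**Step 2: single tests.** The variance of A3−A2 is 2(1−ρ), and of the pooled contrast 1.5(1−ρ). For n = 24, ρ = 0.5, g = 0.2 the noncentralities are:
- pooled: 0.3/√(0.75/24) = 1.70, significant in 37% of trials;
- A3−A2: 0.2/√(1/24) = 0.98, significant in 15% (23% at ρ = 0.7).

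**Step 3: adding the conditions, by simulation (Assessment 3 as third testing).** False confirmation in %, ρ = 0.5/0.7, with A1 v A2 non-significant. Pairwise means A3 significantly above each of A1 and A2.

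| Gain at 2nd, 3rd testing (SD) | Pairwise, n=24 | Pooled, n=24 | Pairwise, n=15 | Pooled, n=15 |
|---|---|---|---|---|
| 0.2, 0.2 | 11.3/18.4 | 31.3/42.9 | 6.6/10.9 | 21.5/30.8 |
| 0.2, 0.1 | 4.4/6.6 | 16.2/22.4 | 2.8/4.2 | 11.5/15.9 |
| 0.1, 0.1 | 3.0/4.9 | 11.6/16.6 | 2.1/2.9 | 8.6/11.5 |
| 0.2, 0 | 1.4/1.6 | 6.7/8.1 | 1.1/1.2 | 5.5/6.6 |
| 0, 0 | 0.4/0.4 | 2.4/2.4 | 0.4/0.5 | 2.3/2.5 |

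**Step 4: the A1 v A2 check.** A significance test flags a 0.2 SD gain in only 15%/23% of trials at n = 24, and 11%/15% at n = 15.

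**Step 5: both Aim 1 contrasts together.** Practice is the same in both arms, so the randomised contrast is falsely favourable in 2.5% of trials, and the joint rate cannot exceed that. At 0.2 SD per retest it is 0.7%/0.9% pairwise and 1.3%/1.6% pooled (n = 24), or 0.4%/0.6% and 1.0%/1.2% (n = 15).

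**Step 6: which testing is Assessment 3.** The Delay sequence is initial, week 9, after the first 8-week block, after the second: four testings, against three elsewhere. The week 9 testing precedes any experience session, so it cannot be the one after Session 16. The length is 8 + 32/2 = 24 weeks at two sessions per week, against about 17 weeks in section 7(l). If Assessment 3 is the fourth testing, the pairwise rate at n = 24 is 39%/56% with 0.2 SD per retest, 7%/11% with gains of 0.2, 0.1 and 0.05 SD, and under 2% if practice stops. The joint pairwise rate at 0.2 SD per retest is then 1.6%/2.0%.

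**The case against.** The strongest reply is that the plan already guards against this. A1 and A2 both enter the contrast, the expectation that they agree is an informal double baseline, and the Assessment-by-Delay interaction compares change between arms and so uses the Delay arm's untrained change. The contrast is listed second and is said only to add to what comes before. All of that stands. A reader might infer that the untrained change is ignored altogether, or that the Aim 1 conclusion is unsound. The documents support neither.

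The inflated rates also rest on an assumed practice gain that continues past the first retest. Given the plan's wording, the pairwise reading is natural, and on it slowing practice gives 4%/7% and practice that stops gives under 2%. The 39%/56% should not be taken as the expected error: it needs undiminished practice over four testings and the fourth to be the one labelled Assessment 3.

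Replacing the pairwise rule by A3−A2 alone would make matters worse. At 0.2 SD per retest it gives 15%/23% against 11%/18%, because the pairwise rule with the check is a stricter subset of it.

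On timing, the week 16 given for the final assessment in section 2(d) may mean week 16 of experience, which removes that part of the conflict. Section 7(l) also allows up to twice the weekly activities. Neither point resolves three against four testings, nor 24 against 17 weeks at the standard pace.

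What survives is that the expectation about A1 and A2 has no test, margin or consequence, and that a single-arm before-after contrast cannot confirm a benefit.

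**Conclusion.** The point holds in a limited form. The second contrast lacks a concurrent control and uses the untrained change only as an unquantified expectation, so it is supportive evidence. At 0.2 SD per retest and n = 24, false confirmation is 11%/18% pairwise and 31%/43% pooled. It falls to under 2% and about 7%/8% if practice stops after the first retest, and stays at or below about 2.5% with no practice. These figures depend on the assumed gains and correlations. False positives on both Aim 1 contrasts together stay at about 2% or less, so only the strength of a supporting statement is affected. The conflict over the number of Delay-arm testings needs no assumption and leaves the contrast undefined until the sections are reconciled.

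**What to change.** 1. Reconcile sections 2(d), 3(b), 3(d) and 7(l), and state from the study records which Delay-arm testing is Assessment 3.
2. Do not pool A1 with A2 as the reference. Report A3−A2 beside the untrained A2−A1, each with a 95% confidence interval. Keep the requirement that A3 also exceed A1, and do not rely on A3−A2 alone.
3. Describe this contrast as supportive, and rest the Aim 1 claim on the randomised evidence already planned: the Assessment-by-Delay interaction and Delay v No Delay at Assessment 2.
4. Date the change and say whether outcome data had been seen, since Continuing Review item 13 reports that data collection is complete and analysis has begun.

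No new data are needed. The supporting claim becomes weaker and less precise. At n = 24 the 95% half-width for A3−A2 is 2.069 × √(2(1−ρ)/24) = 0.42/0.33 SD, against 0.37/0.28 SD for the pooled contrast. The randomised contrast at Assessment 2 also has limited power, which should be disclosed. For 0.5 SD, unadjusted, the noncentrality is 0.5/√(2/n): 1.73 at n = 24 per arm, about 40% power; 1.37 at n = 15 per arm (assumed equal split), about 26%.

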would indicate that experience may be a primary contributor to initial differences in spatial abilities of the DS and TD participants. If improvements are greater for TD children or similar for both groups, it would suggest that initial differences in spatial abilities between groups are not solely due to differences in experience. We will also examine the interaction of Assessment Group Delay complemented with contrasts to explore more closely how participants with DS compare to TD children. For example, we will compare rate of change over Assessments to see if the participants with DS need more experience to reach the same level of performance as the TD children. This may indicate the need for more intensive training for participants with DS to modify spatial ability performance.

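### Aim 2a attributes a whole-sample Assessment × Group effect to training, although that term averages over Delay and mixes training with practice and maturation

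*Combined protocol and SAP*

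**What the plan says.** Section 3(d) states for Aim 2a: "we will apply Multivariate ANOVA to the whole sample to test for the effect of AssessmentGroup". If the effect is significant, "it is indicative that DS and TD participants do not exhibit the same degree of improvement following training". The direction then carries a conclusion about cause. A larger gain in DS "would indicate that experience may be a primary contributor to initial differences in spatial abilities of the DS and TD participants". The other branch begins "If improvements are greater for TD children or similar for both groups", and both of its cases lead to one conclusion: the initial differences are not explained by experience alone.

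The same section introduces Aim 2 with "We will approach Aim 2 in a very similar statistical manner", after an Aim 1 analysis that uses the Delay versus No Delay comparison at Assessment 2. It also plans the Assessment × Group × Delay interaction, "complemented with contrasts to explore more closely how participants with DS compare to TD children".

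Section 2(d) explains what Delay is for. Half of each group "will not begin the spatial ability experience for the 8 weeks following the first assessment and serve as a control for practice effects" on the measures.

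**The concern.** The Delay arm is the design's means of separating training from retest gain. Aim 1 ties its experience claim to that arm. Aim 2a ties its claim to a term that averages over it, and at Assessment 2 half of the sample behind that term has had no training.

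The training reading is safe only if DS and TD participants gain equally from retesting and from growing older. The documents do not say so. The expectation of "higher scores at Assessment 3 than at Assessments 1 and 2 (which should not differ") concerns the DS Delay participants under Aim 1, not DS against TD. The groups are matched on nonverbal ability, but section 7(a) gives ages of 10–30 for DS and 4–9 for TD.

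At stake is the answer to Aim 2, which section 2(b) frames as improvement in response to similar experience. A difference in retest gain could be reported as a difference in response to training, or could hide one.

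**Working it through.** **Inputs.** From the plan: the factors Group, Delay and Assessment (section 3(d)); 24 per cell, N = 96, alpha .05 (Research Involving Children, Section 2(c)); half of each group delayed (section 2(d)); 30 DS and 54 TD consented (Continuing Review, item 5). Assumed, because the documents give no values: SD 1, one correlation ρ of 0.5 or 0.7 between any two assessments, the sizes of dp, an even Delay split of those consented (15/15/27/27), and, except where stated in step 5, Delay Assessment 3 after 16 sessions.

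**1. The plan's own figure.** For four groups and three repetitions the plan gives a detectable f(V) of .27. As a multivariate within-between test, df1 = 6, df2 = 2 × (96 − 4 − 2 + 2) = 184 and λ = 0.27² × 2 × 96 = 14.0. Power is 79.7%, and 80% is reached at 0.271, so the figure reproduces. It is a 6-df test that pools Assessment × Group, Assessment × Delay and the three-way term. The plan gives no power for the three-way term alone; as a 2-df term at N = 96 it needs f(V) = 0.32.

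**2. What each term estimates.** Let P be practice plus maturation per interval, and T1 and T2 the effects of the first and second blocks of experience.

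| Mean change from Assessment 1 | Assessment 2 | Assessment 3 |
|---|---|---|
| No Delay | P + T1 | 2P + T1 + T2 |
| Delay | P | 2P + T1 |
| Average over Delay | P + T1/2 | 2P + T1 + T2/2 |
| No Delay minus Delay | T1 | T2 |

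Assessment × Group compares the third row between DS and TD. With dt the difference in T1, it estimates dp + dt/2 at Assessment 2. At Assessment 3 it estimates 2dp + dt if the second block adds nothing, or 2dp + 1.5dt if it adds as much again. The three-way term compares the fourth row, where P has cancelled.

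**3. Size with equal training effects.** The DS–TD difference is (dp, 2dp), and the two changes have covariance (1 − ρ)[[2,1],[1,2]]. With q = ¼Σ(1/n), λ = 2dp²/{(1 − ρ)q}, tested on 2 and N − 5 df. Here q = 1/24 at 24 per cell and 0.0519 at 15/15/27/27.

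| Cells | dp per retest | λ (ρ = 0.5, 0.7) | Significant |
|---|---|---|---|
| 24 each | 0.1 SD | 0.96, 1.60 | 12.6%, 18.3% |
| 24 each | 0.2 SD | 3.84, 6.40 | 38.9%, 59.8% |
| 15/15/27/27 | 0.1 SD | 0.77, 1.29 | 11.0%, 15.4% |
| 15/15/27/27 | 0.2 SD | 3.09, 5.14 | 31.9%, 50.0% |

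**4. When the conclusion about experience changes (24 per cell).**
- Extra TD gain with equal training supports a wrong statement about training but stays in the same branch of the plan.
- Extra DS gain of 0.1 or 0.2 SD per retest gives significance in favour of DS in 12–18% or 38–60% of simulated trials.
- Extra TD gain can mask a true DS training advantage of 0.4 SD. If the second block adds nothing, power falls from 39–60% to 13–18% at 0.1 SD, and to 5% at 0.2 SD, which is an exact cancellation point. If the second block adds as much again, power falls from 75–94% to 42–64% and 15–23%.

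**5. The three-way term.** Here q = Σ(1/n) = 4/24 = 1/6. With equal training effects and both arms on the same retests and intervals, it rejects in 5% of trials whatever dp is. If Delay Assessment 3 instead follows Session 32, that arm has one more retest, the Assessment 3 element is dp in size, and λ = (2/3)dp²/{(1 − ρ)/6} = 4dp²/(1 − ρ). This is 0.08 and 0.13 at 0.1 SD, and 0.32 and 0.53 at 0.2 SD. Rejection is 5.6–6.0% and 7.4–9.1%; for the two-way term under that reading it is 18–27% and 58–81%. Under the 16-session reading, power for dt = 0.4 SD comes from λ = (2/3)(0.16)/{(1 − ρ)/6} = 1.28 and 2.13, giving 15–23%; at 15/15/27/27 it is 13–19%.

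**6. The Assessment 2 contrast between groups (24 per cell).** SE = s × √(4/24) = 0.408s.

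| Form | s | 80% power at (ρ = 0.5, 0.7) | 95% CI half-width |
|---|---|---|---|
| Adjusted for Assessment 1 | √(1 − ρ²) | 1.00, 0.83 SD | 0.70, 0.58 SD |
| Change score | √(2(1 − ρ)) | 1.16, 0.90 SD | 0.81, 0.63 SD |
| Unadjusted | 1 | 1.16 SD | 0.81 SD |

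**The case against.** The strongest reply is that the plan already contains the remedy: it includes the three-way term with contrasts and says that Aim 2 follows the Aim 1 approach. That stands. A reader might infer that the Delay arm is ignored under Aim 2, and the documents do not support that. What remains is that the three-way term is there for closer exploration, while the stated conclusions hang on the two-way term.

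The wording is also hedged, and dp is hypothetical. Matching on nonverbal ability may make it smaller, and section 2(b) plans to relate improvement to chronological age. Hedging does not remove the confounding, however. Matching does not establish equal retest gain, and relating total improvement to age does not separate training from practice.

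It is fair to say that Assessment × Group correctly rejects its own null hypothesis when dp is not zero. The error lies in the attribution, not in an inflated type I error of the test.

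Finally, a reader might take the three-way term to be immune to practice effects in all circumstances. Section 2(d) does not allow that. It gives every participant two further assessments, after Sessions 16 and 32. It also gives Delay participants an untrained second assessment followed by the full sequence, which makes four in all. Only the Assessment 2 contrast is free of practice and maturation under both readings, and then only if the arms have equal intervals to Assessment 2.

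**Conclusion.** The concern holds as a fault of interpretation that should be corrected before results are written up. The Aim 2a term measures total differential change and supports a training claim only if dp = 0. With the assumed SD, correlation and 16-session reading, and equal training effects, gaps of 0.1 and 0.2 SD per retest would yield a result misattributed to training in 13–18% and 39–60% of trials at 24 per cell, and in 11–15% and 32–50% at 15/15/27/27.

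These rates illustrate sensitivity; they do not predict this trial's result. A reader might infer that faster maturation in the younger TD children biases the result in a known direction. The documents give neither the size nor the direction of dp. The plan's conclusion about experience changes only if extra DS retest gain mimics a DS advantage or extra TD gain masks a true one.

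**What to change.** - Describe Assessment × Group as total differential change (training plus practice plus maturation). Remove the training attribution and the inference about experience from it.
- Base claims about differential response to training first on the DS–TD difference in the Delay versus No Delay contrast at Assessment 2, with a 95% CI. Adjustment for Assessment 1 is optional. Use the planned Assessment × Group × Delay term as support.
- Reconcile the statements in section 2(d) on when Delay participants have Assessment 3.
- Do not conclude that the groups improve similarly from a non-significant result.
- Label the change as made after data collection, since Continuing Review item 13 reports collection complete and analysis in progress.

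No new data or model term is needed. The cost is precision, as steps 5 and 6 show, and the report should say so. For the change from Assessment 1 to 2 alone, moving from the pooled comparison to the Delay contrast loses no power, because effect and standard error both double.

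Two caveats belong in the report. The faster schedule offered in section 7(l) may make intervals unequal between arms, because the text does not say whether the Delay wait shortens too. The six TD children added to match the arms (Research Involving Children, Section 2(c)) may mean that the TD arm comparison is not purely randomised.
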